3.5.4 Postoperative Withdrawal

A postoperative withdrawal is a Subject who has signed the Informed Consent Form and has been randomized, has received the standard of care study devices, and is later withdrawn from study participation (i.e. withdrawal of consent, revision, death, etc.). See **Table 3-3** below for more examples. All data obtained up to the date of withdrawal will be included in the clinical analysis.

Example	Actions	Follow-up
Subject withdraws	Document Subject's request for withdrawal from the study and Complete End of Study/Withdrawal CRF	Do not continue
consent		
Death	Complete Adverse Event CRF and Complete End of	Do not continue
	Study/Withdrawal CRF	
Revision	See Section 3.5.5 below for more information	Do not continue if the
		metal cup or stem has
		been revised.

Table 3-3: Postoperative Withdrawal Examples

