3.5.5 Revisions/Reoperations

Confidential Version Date: 040CT2021 A revision is defined as a surgical procedure of the affected hip where one or more of the THA components (acetabular cup, femoral stem, femoral head, or liner) are removed. In the event that a Subject must undergo revision of either the stem or the cup before completing the study, the Subject will be withdrawn from study participation and an Adverse Event (AE)/Serious Adverse Event (SAE) CRF and an End of Study/Withdrawal CRF should be completed. *In the event that the head or the liner is exchanged, but the cup and stem are not revised, the subject should remain in the study and continue to be followed.*

A reoperation is defined as any surgical procedure of the affected hip in which no THA components are removed. These subjects are not to be withdrawn. An Adverse Event (AE) CRF must be completed in this case. See **Table 3-4** below for more information on revisions and reoperations.

Table 3-4: Revision and Reoperation Examples

Revision – A surgical procedure of the affected hip where one or more of the THA components (acetabular cup, femoral stem, femoral head, or liner) are removed.

participation					
Example	Actions	Follow-up			
Removal or revision of the acetabular cup	Complete Adverse Events (AE) CRF and End	Do not			
implant	of Study/Withdrawal CRF	continue			
Revision of the femoral stem implant	Complete Adverse Events (AE) CRF and End	Do not			
	of Study/Withdrawal CRF	continue			
Exchange of the liner	Complete Adverse Events (AE) CRF	Continue			
		follow up			
Reoperation – Any surgical procedure of the affected hip in which no THA components are removed					
Example	Actions	Follow-up			
Irrigation and debridement with no	Complete Adverse Events (AE) CRF	Continue			
components removed		follow up			
Surgical reduction of hip after dislocation	Complete Adverse Events (AE) CRF	Continue			
		follow up			

If the acetabular cup or femoral stem is revised, the Subject is to be withdrawn from study participation

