4.2 Secondary Objectives, Endpoints, and Associated Hypotheses

If the primary endpoint analysis successfully demonstrates non-inferiority of mean femoral broaching time, then the following secondary endpoints will be assessed with formal hypotheses, in order, under a gatekeeping strategy

- Non-inferiority of skin-to-skin OR time when KINCISE is used vs. when KINCISE is not used.
- Non-inferiority of the percent of subjects with optimal acetabular cup abduction angle when KINCISE is used vs. when KINCISE is not used.
- Non-inferiority of the percent of subjects with optimal acetabular cup version angle when KINCISE is used vs. when KINCISE is not used.

In addition, the following secondary endpoints do not have prospectively planned hypotheses; these will be summarized for both treatment groups:

- Harris Hip Score (HHS) and HHS change from preoperative baseline
- Forgotten Joint Score (FJS) and FJS change from 6-week postoperative baseline
- EQ-5D-5L and changes in these assessments from preoperative baseline
- Pain (Groin, Thigh, and Buttock)
- Patient Satisfaction
- Post-op time when functional activities can be accomplished (return to work; self-care; etc.)
- Radiographic Outcomes (based upon: AP Hip, AP Pelvis, and Lateral)

Confidential Version Date: 040CT2021

DePuy Synthes Protocol DSJ_2019_03 / Version 2.0 / TV-eFRM-02920 Page **21** of **53**

- Length of hospital stay after index THA
- Re-hospitalizations during the study (including a specific summary of re-hospitalizations within 90 days)
- Narcotic drug usage throughout the study (patient reported)
- Complications (including a specific summary of complications within 90 days post-surgery)

5 Study Design

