AEs should be reported beginning from the start of surgery (*i.e.,* first incision) until Subject participation has ended (study completed, or consent withdrawn). When a Subject ends participation in the trial (either study completion or consent withdrawal) all open AE outcomes must be designated as "Recovered/Resolved with no residual effects", "Recovered/Resolved with residual effects", "Ongoing", "Death", or "Unknown" providing a resolution date or ongoing designation.

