10.4 Handling of Missing Data

Missing data will be assumed missing at random. Actual subject data which is collected will be utilized in analyses to determine the outcome of the analyses for all endpoints.

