8.2 Disposition of Study Subjects

Counts of the following categories of subjects by treatment and in total will be provided: All Enrolled dataset, Safety, major inclusion/exclusion protocol violations, Per Prototol, non inclusion/exclusion major protocol violations, deaths, withdrawals, study completion, ongoing in the study.

A subject accounting table using the Safety set will also be provided to account for the following at each follow-up interval:

- Treated: the count of subjects treated; This should not vary per visit;
- Not Yet Due: the count of subjects who do not have an evaluation at the visit (Harris Hip or Forgotten Joint) and who, based on date of surgery and date of data extract, are not yet in-window for the visit;
- Theoretical Due: the count of subjects treated and not counted in Not Yet Due;
- Death: the count of theoretical subjects who died after the start of the window and who do not have data (Harris Hip or Forgotten Joint) at the visit;
- Revision: the count of subjects theoretically due, without data at the visit, who were revised and withdrawn from the study;
- Not Yet Overdue: count of theoretical subjects within the evaluation time window;
 Do not count subjects who have data at the visit or subjects who are counted in
 Death or Revision;
- Expected: the count of subjects theoretically due who are not counted in Death, Revision, Not Yet Overdue;
- Actual data on file (records with a date): the count of subjects with a record with a date for each of the following endpoints: RSA measured subsidence, cup positioning at 6 weeks, Harris Hip, HOOS Jr., Forgotten Joint score, and Linear head penetration. A count of subjects with a record with a date in any of the listed

endpoints will also be provided and a follow-up rate will be calculated using the number of expected subjects in the interval as denominator;

- -
- Any data on file: the count of subjects with any record with a date for the endpoints listed in "Actual data on file"
- Follow-up rate calculated as 100*(Any data on file)/Expected

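### SAP 8.2 builds the follow-up-rate denominator with faulty date limits for deaths and revisions, and Protocol 3.5.5 ends data collection at stem or cup revision, leaving the 90-day and 24-week summaries incomplete

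*Protocol*

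**What the plan says.** **Follow-up after revision.** Under Protocol 3.5.5, on "revision of either the stem or the cup before completing the study, the Subject will be withdrawn from study participation". Tables 3-3 and 3-4 mark these subjects as not continuing. If only the head or liner is exchanged, "the subject should remain in the study and continue to be followed", and reoperations that remove no component are also followed. The revision is recorded on an AE/SAE form. Protocol 3.5.4 adds: "All data obtained up to the date of withdrawal will be included in the clinical analysis".

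**Endpoints that run past a revision.** Protocol 4.2 lists "Re-hospitalizations during the study (including a specific summary of re-hospitalizations within 90 days", a matching item for complications, and the Harris Hip, Forgotten Joint and EQ-5D-5L scores. None of these has a hypothesis. Protocol 10.9.5 places the 90-day summaries under the safety analyses, on the Safety Population. For missing data, Protocol 10.4 says "Missing data will be assumed missing at random". SAP 8.11 rules out imputation and SAP 8.13 rules out sensitivity analyses.

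**Subject accounting.** In SAP 8.2, *Theoretical Due* is every treated subject not classed as *Not Yet Due*. *Expected* is *Theoretical Due* less *Death*, *Revision* and *Not Yet Overdue*, and it is the denominator of the follow-up rate. Two of those rows read:
- "Death: the count of theoretical subjects who died after the start of the window and who do not have data"
- "Revision: the count of subjects theoretically due, without data at the visit, who were revised and withdrawn from the study"

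**The concern.** There are two separate faults.

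The first is arithmetic. A subject should leave a visit's denominator only if death or withdrawal made that visit impossible. The *Death* row has a lower date limit, the start of the window, where it needs an upper one. The *Revision* row has no date limit. Some subjects who could not attend are therefore still expected, and some who could have attended are excused.

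The second concerns data collection. KINCISE is used to prepare the femur and to impact the stem and cup (Protocol Section 1), and observation stops when one of those two components is revised. A subject revised early stays in the Safety Population denominator but cannot contribute a later event, and no censoring or person-time method is given. The 24-week means cover only subjects who kept both components. At stake are the completeness of the by-arm descriptive safety summaries and what the 24-week scores describe.

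**Working it through.** The documents state no revision rate, death rate or expected follow-up rate, so there is no figure of the plan's own to reproduce on this point. The inputs are the SAP 8.2 definitions, the visit windows in SAP Section 4 (6 weeks: days 14 to 60; 24 weeks: days 61 to 200) and the planned 400 subjects, 200 per arm. Every rate below is an assumption.

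**Step 1. Apply the definitions at the final data extract**, when no visit is still pending.

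| Subject | Visit | SAP 8.2 result | Correct result |
|---|---|---|---|
| Died day 40, no 24-week data | 24 weeks | Death precedes day 61, so not in *Death*; stays *Expected* | Remove |
| Died day 100, missed 6-week visit | 6 weeks | Death is after day 14, so in *Death*; removed | Keep: alive throughout days 14 to 60 |
| Revised day 150, missed 6-week visit | 6 weeks | No date condition, so in *Revision*; removed | Keep: not yet revised |
| Revised and withdrawn day 30, no 24-week data | 24 weeks | Removed | Remove, under the current withdrawal rule |

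The first error lowers the rate; the second and third raise it. The last row is not an error.

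**Step 2. Size of the error in the follow-up rate.** Rate = 100 × (any data on file) / *Expected*. One misplaced subject in 400 is 1/400 = 0.25 points.

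- *24 weeks.* Assume 2% revised (8) and 0.5% dead (2), all before day 61, leaving 390; with about 5% of those missing the visit, 370 have data. SAP 8.2 gives 370/(400 − 8) = 94.39%. Removing the two deaths as well gives 370/390 = 94.87%. Across deaths of 0 to 0.5%, revisions of 0.5% to 3% and 5% to 10% missed visits, the SAP figure is 0 to about 0.5 points too low.
- *6 weeks.* Assume 380 of 400 seen, so the rate should be 95.00%. If 1, 2, 4 or 8 of the 20 who missed were revised or died after day 60, SAP 8.2 gives 380/399 = 95.24%, 380/398 = 95.48%, 380/396 = 95.96% or 380/392 = 96.94%. That is 0.2 to 1.9 points too high. The upper end needs 8 of 20 missed visits to be followed by death or revision.

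**Step 3. Size of the effect on 24-week means.** Let a fraction r be revised, and suppose those subjects would score g points below the unrevised mean m. The mean over everyone is (1 − r)m + r(m − g) = m − rg, so leaving them out overstates it by rg.

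- r = 1% to 3% (400 × 0.01 = 4 to 400 × 0.03 = 12 subjects) and g = 30: 0.3 to 0.9 Harris Hip points.
- Wider range, r = 0.5% to 3% and g = 20 to 60: 0.005 × 20 = 0.1 to 0.03 × 60 = 1.8 points.
- With equal revision rates and equal g, the shift cancels between arms. If all 4 to 12 fell in one arm, r there is 4/200 = 2% to 12/200 = 6%, and with g = 30 the difference between arms moves by 0.6 to 1.8 points.

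**Step 4. The 90-day summaries.** A subject revised on day 30 counts in the Safety Population but is unobserved on days 31 to 90, which is 60 of the 90 days.

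**Step 5. Endpoints with hypotheses.** Broaching time and skin-to-skin time are recorded during surgery, before any revision. Cup angles need a postoperative film. Assume 92% on target in 200 controls, and 178 on target among 194 KINCISE subjects with films, six having been revised first.

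- Six left out: 178/194 − 0.92 = −0.25 points; SE = √(0.9175 × 0.0825/194 + 0.92 × 0.08/200) = 0.0275; lower limit = −0.0025 − 1.645 × 0.0275 = −4.8%.
- Six counted as off target: 178/200 − 0.92 = −3.0 points; SE = √(0.89 × 0.11/200 + 0.92 × 0.08/200) = 0.0293; lower limit = −0.030 − 1.645 × 0.0293 = −7.8%.

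Both limits are above −10%.

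**The case against.** The strongest reply is that little of inferential weight is exposed. The primary endpoint is intraoperative, the 24-week scores are descriptive, and describing unrevised hips is a legitimate choice of estimand. That stands. One reservation is that the Per Protocol set requires at least one post-operative visit, and the documents do not say whether discharge counts, so the standing of a subject revised very early is unclear.

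Four stronger readings are tempting but not supported.

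- *That SAP 8.2 makes events or scores vanish.* It is an accounting table and feeds only the follow-up rate. The later data are absent because of the withdrawal rule. For deaths before day 61 the table retains subjects; it does not remove them.
- *That Protocol Section 8 conflicts with 3.5.5.* Section 8 runs AE reporting "until Subject participation has ended (study completed, or consent withdrawn", and a reader might say a revised subject has done neither. But Protocol 7.5, headed Study Completion, lists cup or stem revision among its reasons, and 10.9.5 counts AEs until participation finishes. The parenthesis is loosely worded; it does not contradict 3.5.5.
- *That missing-at-random is contradicted.* That assumption lets missingness depend on observed data, and the revision is observed. The fair criticism is narrower: available-case means describe unrevised hips, and nothing in the plan shows the alternative.
- *That an arm with more revisions would look better on event counts.* Each revision is itself reported as an AE or SAE, AEs are summarised by arm with a listing (SAP 8.9), and withdrawals are counted by arm (SAP 8.2). Excess revisions would be visible. Only what follows them is lost.

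**Conclusion.** Both parts hold within limits.

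The SAP 8.2 date rules are wrong as written. The reported follow-up rate can err in either direction, by about 0.25 points per misplaced subject in 400. Under the assumed ranges it is 0 to 0.5 points too low at 24 weeks and 0.2 to 1.9 points too high at 6 weeks. Nothing beyond that rate is affected.

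The withdrawal rule is a design choice that loses later AEs, later re-hospitalisations and 24-week scores in subjects whose stem or cup is revised. The 90-day safety summaries are incomplete for them, and the 24-week means apply to unrevised hips. The effect on means is small: 0.3 to 0.9 Harris Hip points under assumed revision rates of 1% to 3% and an assumed 30-point deficit. That revised hips would score worse is itself an inference; the documents do not say so. No tested conclusion is shown to change. The case for acting is that complete by-arm safety data can be had at little cost, in a randomised device comparison without a data monitoring committee (SAP Section 9).

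**What to change.** **SAP 8.2.** Define *Death* as died on or before the last day of the visit window, without data at that visit. Define *Revision* as revised and withdrawn on or before the last day of the visit window, without data at that visit. These two definitions resolve every case in the table. The cost is two lines of SAP text and the matching program code.

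**Protocol 3.5.5, Tables 3-3 and 3-4, and the revision item in 7.5.** After stem or cup revision, keep the subject in data collection for AEs, re-hospitalisations and questionnaires to 24 weeks unless consent is withdrawn, and stop only the implant-specific radiographic measures. Summarise the 24-week scores with and without revised hips. This changes data collection, not treatment.

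**Keep the two changes consistent.** If the protocol change is adopted, revised subjects remain *Expected* for questionnaires. The *Revision* row then applies only to subjects who actually left the study, or to the radiographic measures.

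The cost is a protocol amendment and a few extra contacts on existing forms. The downside is that 24-week scores may look slightly less favourable. If the sponsor prefers to keep the withdrawal rule, the report should say that the 24-week means describe unrevised hips and that 90-day events are observed only up to revision.

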3.5.6 Minimization of Subjects Lost to Follow-up

Although follow up compliance is essential to study quality, some Subjects may not be able or willing to return for their scheduled follow-up evaluations as prescribed in the protocol. Given the short duration of the follow-up for this study, this is not expected to occur often.

Sites should make every effort to ensure complete follow-up whenever possible through phone calls and written requests to a Subject. Each Investigator must maintain a record of communications and/or attempts at communication in the source documentation.

A subject can be classified as "lost-to-follow-up" and subsequently withdrawn from the study only after the site has documented in the medical record at least two unsuccessful attempts of contact.

Figure 3-1: Screening, Enrollment and Randomization Process

Confidential Version Date: 040CT2021 DePuy Synthes Protocol DSJ_2019_03 / Version 2.0 / TV-eFRM-02920 Page **20** of **53**

4 Objectives, Endpoints, and Associated Hypotheses

4.1 Primary Objective, Endpoint, and Associated Hypotheses

The primary endpoint is the mean femoral broaching in minutes collected intraoperatively. Femoral broach time should be collected intraoperatively in minutes and seconds and should begin at the time the box osteotome first enters the femoral canal and end with seating of the final broach trial within the femoral canal.

The primary objective of this study is to demonstrate that the mean femoral broaching time with KINCISE is non-inferior to the mean femoral broaching time with manual instruments when used in THA with Anterior Advantage.

If non-inferiority is successfully demonstrated then the study will be deemed successful, and a test for superiority for mean femoral broaching time will be conducted.

4.2 Secondary Objectives, Endpoints, and Associated Hypotheses

If the primary endpoint analysis successfully demonstrates non-inferiority of mean femoral broaching time, then the following secondary endpoints will be assessed with formal hypotheses, in order, under a gatekeeping strategy

- Non-inferiority of skin-to-skin OR time when KINCISE is used vs. when KINCISE is not used.
- Non-inferiority of the percent of subjects with optimal acetabular cup abduction angle when KINCISE is used vs. when KINCISE is not used.
- Non-inferiority of the percent of subjects with optimal acetabular cup version angle when KINCISE is used vs. when KINCISE is not used.

In addition, the following secondary endpoints do not have prospectively planned hypotheses; these will be summarized for both treatment groups:

- Harris Hip Score (HHS) and HHS change from preoperative baseline
- Forgotten Joint Score (FJS) and FJS change from 6-week postoperative baseline
- EQ-5D-5L and changes in these assessments from preoperative baseline
- Pain (Groin, Thigh, and Buttock)
- Patient Satisfaction
- Post-op time when functional activities can be accomplished (return to work; self-care; etc.)
- Radiographic Outcomes (based upon: AP Hip, AP Pelvis, and Lateral)

Confidential Version Date: 040CT2021

DePuy Synthes Protocol DSJ_2019_03 / Version 2.0 / TV-eFRM-02920 Page **21** of **53**

- Length of hospital stay after index THA
- Re-hospitalizations during the study (including a specific summary of re-hospitalizations within 90 days)
- Narcotic drug usage throughout the study (patient reported)
- Complications (including a specific summary of complications within 90 days post-surgery)

5 Study Design

5.1 Study Design Summary

This is a post-market randomized, prospective, multi-center study with a planned analysis of 400 subjects (200 per treatment group). Up to 20 study sites will be approved to participate in this study. Each site is expected to enroll the number of subjects as outlined in their clinical trial agreement. It is anticipated that each site will enroll approximately 20 subjects per arm (40 subjects total). Reallocation of patients may occur to allow completion of study enrollment in a timely manner. Sites may replace Subjects that are screen failures and preoperative or intraoperative withdrawals to ensure adequate numbers for final analysis.

Competitive enrollment will be utilized and managed by the sponsor. The sponsor will communicate to each site regarding increased or decreased enrollment allotment and each site should anticipate enrolling 40 total subjects (20 per arm) unless it is communicated otherwise. Details regarding sample size are presented below in **Section 10.8**.

Each site will use the Pinnacle cup and the stem (Corail or Actis uncemented) that fit with their standard of care. The devices used in this study are available to all patients needing uncemented THA whether they choose to be a part of the study or not, since this is a post-market study.

5.2 Study Database

The study database has been validated in accordance with 21 CFR Part 11. Prior to being released for importation of study data, validation of the study level components will be conducted in accordance with approved user acceptance testing procedures. Access to this system will be controlled so that only authorized users will have the ability to enter into the system. The system is considered a closed system according to 21 CFR Part 11 Electronic Records; Electronic Signatures.

6 Radiographs

The radiographs collected for this study will be sent to Medical Metrics, Inc. (MMI) for third party review. This study will accept radiographs for the preoperative interval taken prior to the study Subject's participation in this study up to 180 days before surgery as long as the radiographs meet the three

Confidential Version Date: 040CT2021 DePuy Synthes Protocol DSJ_2019_03 / Version 2.0 / TV-eFRM-02920 Page **22** of **53** protocol required views: Antero-Posterior (AP) Long Leg or AP Pelvis (bilateral), AP Hip (unilateral), and Lateral. Preoperatively, weight-bearing AP Pelvis and AP Hip and Modified Lauenstein views are preferred, but not required. The 180 day preoperative window is allowed in order to minimize a study subject's unnecessary exposure to radiation, therefore, standard of care views will be accepted preoperatively if imaging has already been acquired before the subject was consented for the study. For all post-operative intervals, weight-bearing AP Hip and AP Pelvis, and Lateral films are required. The Modified Lauenstein view is preferred postoperatively but a Lauenstein lateral or cross-table lateral view will be accepted in instances where the view cannot be collected due to subject positioning constraints. Further radiographic details will be available in the radiographic protocol separate to this document.

7 Subject Evaluations

This section details the pre-operative, operative, and post-operative management of Subjects. This study does not limit the procedures involved in the treatment of the subject (i.e. all medical care decisions related to the surgery are standard of care and at the discretion of the surgeon). The pre-operative, anesthesia, operative procedures, post-op care, and follow up are not research procedures, and therefore are not restricted by the study and are regardless of the research. This study will collect data from the standard of care medical treatments and requires the following research related activities: Subject self-assessments (Forgotten Joint Score, EQ-5D-5L, Hip Evaluation), Harris Hip Evaluation (if not already standard of care), preoperative planning details, radiographic evaluations, radiographic imaging (some study-required views might be outside site standard of care).

